### 7.1 Efficacy Analysis Sets

A summary of efficacy analysis sets is presented in Table 7-1.

Table 7-1 Summary of Efficacy Analysis Sets

Efficacy Set	Purpose	Studies	Treatment Label §
Study 102 FAS	To evaluate efficacy data during study 102	659-102	VX-659/TEZ/IVA in 659-102 PBO in 659-102
Study 103 FAS	To evaluate efficacy data during study 103	659-103	VX-659/TEZ/IVA in 659-103 TEZ/IVA in 659-103
OL Full Analysis Set (OL-FAS)	To evaluate efficacy data during study 105	659-105	VX-659/TEZ/IVA in 659-102 PBO in 659-102 VX-659/TEZ/IVA in 659-103 TEZ/IVA in 659-103 Any VX-659/TEZ/IVA †
Cumulative TC Efficacy Set	To evaluate PEx data on VX-659/TEZ/IVA during the parent study or during study 105	659-102 659-103 659-105	VX-659/TEZ/IVA in 659-102 PBO in 659-102 Any VX-659/TEZ/IVA

† does not apply for MMRM and descriptive summary of continuous efficacy endpoints

§ Treatment label is based on the treatment the subject was assigned to in the parent study. The “Any VX-659/TEZ/IVA” group refers to all the subjects in the corresponding analysis set.

### 7.1.1 Parent Study Efficacy Analysis Set

The Parent Study Efficacy Analysis Sets are: Study 102 Full Analysis Set (FAS) and Study 103 FAS. The definition of these analysis sets is same as the FAS definition in the SAP for studies 102 and 103.

### 7.1.2 OL Full Analysis Set (OL-FAS)

The OL Full Analysis Set is defined as all enrolled subjects who received at least 1 dose of study drug in the OLS. The OL-FAS will be used for efficacy analysis in those subjects who had participated in study 102, or study 103 and then transitioned to the treatment cohort of study 105. The efficacy data from subjects from the parent study 102 will be presented separately from the efficacy data for subjects from the parent study 103.

### 7.1.3 Cumulative TC Efficacy Set

The Cumulative TC Efficacy Set includes subjects who were randomized to VX-659/TEZ/IVA and received at least one dose of study drug during the parent study and/or received at least one dose of study drug during the OLS. The Cumulative TC Efficacy Set will be used to analyze PEx data on VX-659/TEZ/IVA during the parent study or during study 105. PEx data for subjects from parent study 102 will be presented separately from the PEx data for subjects from parent study 103.

## 7.2 Safety Analysis Set

### 7.2.1 OL Safety Set (OL-SS)

The OL Safety Set is defined as all subjects who received at least 1 dose of study drug in the OLS. The OL-SS will be used primarily for safety analyses during OLS with the treatment label “Any VX-659/TEZ/IVA”.

## 8 ANALYSIS PERIOD

The analysis period used for safety and efficacy endpoints in the final analysis of study 105 is described below. For the IA, the same definition applies but in addition the IA data cutoff date will be considered to ensure that the analysis period does not exceed the IA data cutoff date.

### 8.1 Open Label (OL) Period

**OL Efficacy Period:** Time from the first dose of study drug in the OLS until the last efficacy assessment, which may be collected up to the Week 96 Visit or the earlier of Day 673 and the end of study participation if subject does not have the Week 96 Visit. This analysis period will be used with the OL-FAS to analyze efficacy data during the OLS.

**OL Safety Period:** The time from the first dose of study drug in the OLS to 28 days after the last dose date of the study drug in the OLS or to the completion date of study participation (Section 9.1.5 of the study 105 CSP), whichever occurs first. This analysis period will be used with the OL-SS to analyze the safety data during the OLS.

### 8.2 Cumulative TC Efficacy Period

For subjects who enrolled in the OLS, the time from the first dose of study drug in study 102 or study 103 (for subjects randomized to VX-659/TEZ/IVA in these studies) or in study 105 (for subjects not randomized to VX-659/TEZ/IVA in these studies) until the last efficacy assessment, which may be collected up to the Week 96 Visit or the earlier of Day 673 and the end of study participation if subject does not have the Week 96 Visit. For subjects who did not enroll in the OLS and were randomized to VX-659/TEZ/IVA in studies 102 or 103 and received study drug in the parent study, definition of this analysis period is the same as the parent study efficacy period. The cumulative TC Efficacy period for subjects from studies 102 and 103 who enrolled in the OLS is represented by the shaded portion in [Figure 8-1](#). The cumulative TC Efficacy period will be used with the cumulative TC Efficacy set for analysis of PEx data. Note that the data between SFUV of parent study and OLS informed consent form signing will not be collected when there is a gap in time between these two milestones; the corresponding duration will be excluded from the cumulative TC Efficacy period.

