^j Subjects will have a complete physical examination as defined in Section 11.7.3. Symptom-directed physical examinations will occur at any time during the study if deemed necessary by the investigator.

^k Pregnancy tests will be performed for all female subjects of childbearing potential as described in Section 11.7.2. At assessment time points when telephone contact takes the place of a clinic visit, a urine pregnancy test will be performed with a home kit provided by the study site. Results will be reported to the site by telephone.

^l Blood samples for FSH will be measured as outlined in Section 11.7.2

^m All standard 12-lead ECGs will be performed after the subject has been at rest for at least 5 minutes. ECGs will be collected before dosing (as applicable).

ⁿ Vital signs and pulse oximetry will be collected before dosing and after the subject has been at rest for at least 5 minutes (Section 11.7.3 and Section 11.7.4).

^o Spirometry assessments must be performed before study drug dosing (Section 9.6.1) and should be performed pre-bronchodilator (Section 11.6.1) at approximately the same time each visit.

^p Sweat chloride collection will occur before study drug dosing (Section 11.4). At each time point, 2 samples will be collected, 1 from each arm (left and right).

^q PK samples will be collected predose on Week 4 only as described in Section 11.3.1.

Table 3-1 VX17-659-105: Treatment Period and Safety Follow-up Visit

Event/Assessment ^a	Treatment Period							ETT Visit ^c	Safety Follow-up Visit (28 ± 7 Days After Last Dose) ^d
	Day 1 ^b	Day 15 (± 3 Days)	Weeks 4, 8, 16, 24, 36 (± 5 Days)	Weeks 12, 20, 28, 32, 40, 44, 52, 56, 64, 68, 76, 80, 88, 92 (± 5 Days)	Week 48 (± 5 Days)	Weeks 60, 72, 84 (± 5 Days)	Week 96 (± 5 Days)		
Study drug count	X	X	X		X	X	X	X	
Study drug dosing ^s	Day 1 through evening before Week 96 Visit								
Other events related to outcome ^t	Continuous from signing of the ICF through completion of study participation								
Medications review ^u	Continuous from signing of the ICF through completion of study participation								
Treatments and procedures review ^u	Continuous from signing of the ICF through completion of study participation								
AEs and SAEs ^{u, v}	Continuous from signing of the ICF through completion of study participation								

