AE: adverse event; BMI: body mass index; CF: cystic fibrosis; CFQ-R: CF Questionnaire-Revised; ETT: Early Termination of Treatment; FSH: follicle stimulating hormone; GPS: Global Patient Safety; ICF: informed consent form; PEx: pulmonary exacerbation(s); PK: pharmacokinetic; SAE: serious adverse event; SwCl: sweat chloride

^s The study drug regimen should be administered as outlined in Section 9.6.1. On days of scheduled visits, refer to Section 9.6.1 for the timing of dosing relative to the assessments. The final dose of study drug will be administered the evening before the Week 96 Visit.

^t Other events related to outcome include assessments relating to PEx, administration of antibiotic therapy for sinopulmonary signs/symptoms, and hospitalizations for CF (Section 11.6.4).

^u Completion of study participation is defined in Section 9.1.5.

^v SAEs that occur after completion of study participation and are considered related to study drug will be reported to Vertex GPS within 24 hours as described in Section 13.1.2.2.

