9.1.2 Safety Follow-up

The Safety Follow-up Visit is scheduled to occur 28 (\pm 7) days after the last dose of study drug. The Safety Follow-up Visit assessments are listed in [Table 3-1](#).

The Safety Follow-up Visit is required for all subjects. However, subjects who transition within 28 days of the last dose of study drug to either a commercially available or managed access program-supplied next-generation corrector TC regimen, or to another qualified Vertex study, will complete the Week 96 Visit (or the ETT Visit, if the transition occurs before the Week 96 Visit). In these cases, the Week 96 Visit (or the ETT Visit) will replace the Safety Follow-up Visit. For subjects who complete an ETT Visit 3 weeks or later following the last dose of study drug, the ETT Visit will replace the Safety Follow-up Visit (Section 9.1.3).

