9.1.5 Completion of Study Participation

Completion of study participation for each individual subject is defined as: the Safety Follow-up Visit; or, in situations in which the ETT Visit or the Week 96 Visit replace the Safety Follow-up Visit (Section 9.1.2), the ETT Visit or the Week 96 Visit.

If subjects withdraw consent or assent, completion of study participation is defined as date of withdrawal of consent or assent, whichever is earlier (Section 9.9).

If subjects are lost to follow-up (Section 9.1.4), the date of completion of study participation will be defined as the date of last contact.

The end of study is defined in Section 13.2.8.

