12.3 Statistical Analysis

12.3.1 General Considerations

Continuous variables will be summarized using the following descriptive summary statistics: the number of subjects (n), mean, SD, median, minimum value (min), and maximum value (max). The precision of the measurement for each continuous variable will be specified in the SAP. Unless otherwise specified, min and max values will be reported with the same precision as

the units of the raw data. The mean, median, and SD will be reported to 1 additional decimal place. Any values that require a transformation to standard units (metric or SI) will be converted with the appropriate precision.

Categorical variables will be summarized using counts and percentages. Percentages will be presented to 1 decimal place.

The baseline value, unless otherwise specified, for the long-term safety analysis will be the most recent non-missing measurement (scheduled or unscheduled) collected before the first dose of VX-659 in TC with TEZ/IVA either in the parent study or the open-label study, as applicable. The baseline value for the long-term efficacy analysis will be defined as the most recent non-missing measurement (scheduled or unscheduled) collected before the first dose of study drug in the parent study. For assessments collected in duplicate or triplicate, the baseline will be defined as the average of non-missing values.

Baseline characteristics of subjects in the open-label study will be the same as the baseline characteristics in the parent study.

Change (absolute change) from baseline will be calculated as post-baseline value - baseline value.

The **Efficacy Analysis Period** in the open-label study will include the time from the first dose of study drug in the open-label study to the last scheduled efficacy visit in the open-label study, unless otherwise specified.

The **Treatment-emergent (TE) Period** in the open-label study will include the time from the first dose of study drug in the open-label study to 28 days after the last dose of the study drug in the open-label study or to the completion date of study participation (as defined in Section 9.1.5), whichever occurs first.

The long-term efficacy analysis will be performed by parent study for the Efficacy Analysis Period in the open-label study, with the only exception of time to first PEx where events in the parent study may also be included.

In general, long-term safety analysis will be performed in a pooled fashion.

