12.3.3.2 Analysis of Secondary Variables

The secondary variables include:

- **Absolute change from baseline in ppFEV₁**

One of the secondary efficacy endpoints is the absolute change from baseline in ppFEV₁ at visits in the open-label study, for subjects who receive at least 1 dose of study drug in the open-label study. The primary analysis for this secondary endpoint will be based on a mixed-effects model for repeated measures (MMRM) for each individual parent study, with the absolute change from baseline in ppFEV₁ as the dependent variable for visits in the open-label study.

The details including sensitivity analyses and supportive analysis will be described in the SAP.

- **Absolute change from baseline in SwCI**

Analysis of this PD variable will be based on an MMRM model similar to the analysis of the absolute change from baseline in ppFEV₁.

- **Number of PEx**

The analysis of the number of PEx starting from the first dose of TC in the parent/open-label study will be performed using a negative binomial regression model for each individual parent study, unless otherwise specified.

- **Time-to-first PEx**

Time-to-first PEx is defined as the number of days starting from the first dose of TC in the parent/open-label study to the first event of PEx. Note that for patients who were randomized to placebo or TEZ/IVA group, the first dose of TC will occur in the open-label study. A subject

who does not experience an exacerbation prior to the end of the Efficacy Analysis Period in the open-label study will be considered censored at the end of the Efficacy Analysis Period. The Kaplan-Meier method will be used to produce a graphical presentation of the cumulative exacerbation-free survival rate.

- **Absolute change from baseline in BMI**

Analysis of this variable will be based on an MMRM model similar to the analysis of the absolute change from baseline in ppFEV₁.

- **Absolute change from baseline in BMI z-score**

Analysis of this variable will be based on an MMRM model similar to the analysis of the absolute change from baseline in ppFEV₁.

- **Absolute change from baseline in body weight**

Analysis for this variable will be based on an MMRM model similar to the analysis of the absolute change from baseline in ppFEV₁.

- **Absolute change from baseline in CFQ-R respiratory domain score**

Analysis of this variable will be based on an MMRM model similar to the analysis of the absolute change from baseline in ppFEV₁.

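### For subjects without a Week 96 Visit, the PEx count meant to describe time on triple combination can include weeks off drug; show it split by onset relative to last dose

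*SAP*

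**What the plan says.** SAP Table 7-1 gives the purpose of the Cumulative TC Efficacy Set as "To evaluate PEx data on VX-659/TEZ/IVA during the parent study or during study 105", and SAP 7.1.3 repeats it. SAP 8.2 ends the matching period at the last efficacy assessment, taken up to the Week 96 Visit or, failing that, up to "the earlier of Day 673 and the end of study participation if subject does not have the Week 96 Visit". SAP 9.3.2.2 counts all PEx in that period, and also those with hospitalisation or IV antibiotics. It does not separate events by onset relative to last dose, and SAP 9.3.2.3 plans no supportive analysis.

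The protocol supplies the dates:
- Table 3-1, footnote s: "The final dose of study drug will be administered the evening before the Week 96 Visit".
- Section 9.1.5: "Completion of study participation for each individual subject is defined as: the Safety Follow-up Visit". An ETT or Week 96 Visit counts instead where it replaces that visit. Other rules cover withdrawal and loss to follow-up.
- Table 3-1 and section 9.1.2: Safety Follow-up is 28 ± 7 days after last dose. The exception is "subjects who transition within 28 days of the last dose of study drug" to another next-generation TC regimen or a qualified study of the sponsor; their ETT or Week 96 Visit takes its place.
- Table 3-1, collection of outcome events including PEx: "Continuous from signing of the ICF through completion of study participation".
- Section 9.1.3: an ETT Visit three weeks or more after last dose also replaces Safety Follow-up.

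**The concern.** Two kinds of subject enter one count on different terms. A subject with a Week 96 Visit contributes about one day after last dose, and that subject's Safety Follow-up time is left out. A subject without one can contribute the whole follow-up interval. Spirometry, CFQ-R and weight are scheduled at Safety Follow-up, so it can be the last efficacy assessment that closes the period.

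SAP section 3 says the study was ended early, so the second branch matters. Number of PEx is a listed secondary endpoint and, with the models removed (SAP 9.3), the descriptive count is the planned PEx result. Someone who reads it with the stated purpose in mind could not tell how many events began weeks after stopping.

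A related point concerns the continuous endpoints. SAP Table 12-1 keeps Safety Follow-up values in a separate row by nominal visit. Footnote 2, read literally, places a late ETT Visit in an OL Week window by study day, although that visit stands in for Safety Follow-up.

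**Working it through.** **The plan's own figures.** Day 673 = 96 × 7 + 1, which is Week 96. The PEx precision statement in SAP 6.2 (half-width below 6% at 30% incidence, 400 subjects) reproduces: 1.96 × √(0.3 × 0.7 / 400) = 4.5%. Neither figure is disputed.

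**Off-drug days at the end of the period.**
- With a Week 96 Visit: about 1.
- Without one, last dose on day L and Safety Follow-up d days later: min(L + d, 673) − L. With d = 28 − 7 to 28 + 7, this is 21 to 35 days.
- The Day 673 cap shortens it. A full 28 days needs L ≤ 673 − 28 = Day 645; a last dose on Day 660 leaves at most 13.
- Transition within 28 days or withdrawal of consent can also shorten it. A late ETT Visit can lengthen it, since Protocol 9.1.3 states no upper limit.

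**Effect on the group count.** The documents give neither the share with a tail nor time on drug, so both are assumed. Let f be the share with a 4-week tail and T their weeks on drug; the rest have 96 weeks. The PEx rate is assumed unchanged off drug. Counting open-label time only, the added count relative to the on-drug count is 4f / (fT + 96(1 − f)):

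| T (weeks) | f = 0.25 | f = 0.50 | f = 0.75 |
|---|---|---|---|
| 24 | 1.3% | 3.3% | 7.1% |
| 48 | 1.2% | 2.8% | 5.0% |
| 72 | 1.1% | 2.4% | 3.8% |

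For example, f = 0.75 and T = 24 gives 3 / (18 + 24) = 7.1%.

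**Variations.**
- Tail of 3 to 5 weeks: 0.75/90 = 0.8% up to 3.75/42 = 8.9%.
- Everyone has only 24 weeks on drug and 75% have a tail: 3/24 = 12.5%.
- Share n (0.25 to 0.75) without a Week 96 Visit, half of them with no tail: 2n / (nT + 96(1 − n)), which runs from 0.5/90 = 0.6% to 1.5/42 = 3.6%.
- P parent-study TC weeks added for everyone (assumed), at f = 0.75 and T = 24: P = 4 gives 3 / (21 + 25) = 6.5%; P = 24 gives 3 / (36 + 30) = 4.5%.
- A higher rate after stopping would scale these percentages in proportion; the documents give no such rate.

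**Absolute size.** Read the 30% in SAP 6.2 as a 24-week incidence with constant rate (assumed). The rate is −ln(0.7)/24 = 0.01486 per week, or 0.0594 per 4-week tail. In 400 subjects, f = 0.25, 0.50 and 0.75 give 5.9, 11.9 and 17.8 tail events. On-drug events are 400 × 0.01486 × (fT + 96(1 − f)), from 250 (f = 0.75, T = 24) to 535 (f = 0.25, T = 72).

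**The case against.** The strongest reply is that no stated rule is broken. SAP 8.2 can be read as a common 96-week horizon. Protocol 12.3.1 runs its efficacy period "to the last scheduled efficacy visit in the open-label study, unless otherwise specified", and Protocol 12.3.3.2 describes "The analysis of the number of PEx starting from the first dose of TC in the parent/open-label study"; neither cuts PEx at last dose. The purpose wording in Table 7-1 may only separate time since starting TC from placebo or TEZ/IVA time. Both safety periods run to as much as 28 days after last dose, so a one-day cut could list an event as treatment-emergent in the safety tables and as late in the PEx table. The separate Safety Follow-up row in Table 12-1 suits endpoints summarised by visit, which PEx is not.

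Most of this stands. It bears on the choice of interval and label, however, and not on whether to show the two parts: with both displayed, either reading is served.

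The objection also limits the remedy. SAP 8.2 removes only the gap between the parent study's follow-up visit and open-label consent, and Protocol 9.1.1 allows a first open-label dose more than 7 days after the last parent dose. A split at the final dose alone would leave those parent-to-open-label off-drug days in the first part.

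A reader might infer that the parent-arm comparison is biased, that the SAP contradicts the protocol, or that every early stopper has 21 to 35 off-drug days. The documents support none of these. Every parent arm follows one rule, no formal comparison is planned, the protocol has no last-dose cut, and the range describes only an in-window Safety Follow-up Visit. Nor is the SAP silent on late ETT Visits: footnote 2 covers them, with an awkward result.

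**Conclusion.** The point holds as a cheap improvement to a descriptive secondary endpoint. The period can contain weeks after last dose for subjects without a Week 96 Visit, so the count does not fully match its stated purpose.

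The size is illustrative: about 1% to 7% added to the open-label count, or about 6 to 18 events in 400 subjects. It rests wholly on assumed shares, assumed time on drug and an unchanged rate, and it shrinks once parent TC time or subjects without a tail are counted. Unequal follow-up affects the raw counts more than this tail does. The ETT point touches only late ETT Visits, whose frequency is not given.

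**What to change.** Keep the SAP 8.2 period and the total. In SAP 9.3.2.2:
- Show the PEx, hospitalisation and IV-antibiotic counts by onset: up to one pre-stated fixed interval after the last TC dose, and later within the period. One day matches what the Week 96 rule gives now. An interval of 28 days would match the safety period but leave only days 29 to 35 of an in-window tail in the second part.
- Label the first part as running through last TC dose plus x days, not simply as on TC. Alternatively, also move to the second part any PEx starting between the last parent-study dose (plus the same interval) and the first open-label dose.
- Footnote that dosing interruptions stay in the first part.
- For subjects who did not enter the open-label study, apply the same cut within the parent-study efficacy period.

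In SAP Table 12-1, state that values from an ETT Visit three weeks or more after last dose go to the Safety Follow-up row.

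The cost is one date derivation (a second if parent-study gaps are moved), a table split and footnotes. No new data are needed, because PEx are already recorded to completion of participation. The drawback is that the first count alone omits PEx emerging just after stopping, so both parts must always appear together.

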**Figure 8-1 Cumulative TC Efficacy Period for Subjects who enrolled in the OLS**

Subjects from Study 102

VX-659/TEZ/IVA DB (randomized)	VX-659/TEZ/IVA OLS
Placebo DB	VX-659/TEZ/IVA OLS

Subjects from Study 103

TEZ/IVA Run-in	VX-659/TEZ/IVA DB (randomized)	VX-659/TEZ/IVA OLS
TEZ/IVA Run-in	TEZ/IVA DB	VX-659/TEZ/IVA OLS

DB: double-blind

## 9 STATISTICAL ANALYSIS

### 9.1 General Considerations

The Schedule of Assessments is provided in Section 3 of CSP. The precision standards for reporting safety and efficacy variables are provided in an internal Biometrics document that specifies the programming rules including the precision for derived variables.

**Continuous variables** will be summarized using the following descriptive summary statistics: the number of subjects (n), mean, SD, median, minimum value (min), and maximum value (max).

**Categorical variables** will be summarized using counts and percentages. Percentages will be presented to 1 decimal place.

